### 6.3 Stratification factors and intervention allocation plan for randomized studies

This is not a randomized trial and we will not be stratifying on any variable.

### 6.4 Stratification factors and their impact on design

None.

### 6.5 Early stopping rules, if appropriate

None.

### 6.6 Unevaluable/ineligible participants

Our aim is to evaluate how the device is used in home settings. Therefore, subjects who become hospitalized will stop using the device. If the hospitalized subject has contributed less than 50% of data (i.e. used the device for less than 7 days) prior to hospitalization, they will be dropped from the study and another subject will be recruited to make up the enrollment target. However, subjects who have contributed at least 50% of data prior to hospitalization will stop using the device but will be included in final analyses. We estimate that less than 20% of subjects enrolled in the study might be inevaluable.

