#### ***Registration Process for DF/HCC and DF/PCC Institutions***

The QACT registration staff is accessible on Monday through Friday, from 8:00 AM to 5:00 PM Eastern Standard Time.

The registration procedures are as follows:

- Obtain written informed consent from the participant prior to the performance of any protocol specific procedures or assessments.
- Complete the QACT protocol-specific eligibility checklist using the eligibility assessment documented in the participant's medical record and/or research chart. **To be eligible for registration to the protocol, the participant must meet all inclusion and exclusion criterion as described in the protocol and reflected on the eligibility checklist.**
- Fax the eligibility checklist(s) and all pages of the consent form(s) to the QACT at [contact]. For Phase I protocols, attach participant dose level assignment confirmation from the sponsor.
- The QACT Registrar will (a) review the eligibility checklist, (b) register the participant on the protocol, and (c) randomize the participant when applicable.
- An email confirmation of the registration and/or randomization will be sent to the Overall PI, study coordinator(s) from the Lead Site, treating investigator and registering person immediately following the registration and/or randomization.

5.63 During the study:

- If the study team does not receive data from the iThermonitor by the second day after study enrollment, study staff will follow-up (telephone call) with subjects to ensure that they are able to correctly set-up the device. We will encourage participants to continue to receive medical treatment and adhere to other management protocols as recommended by their physicians as usual. We will emphasize that the iThermonitor does not replace usual temperature monitoring protocols.
- Use the iThermonitor everyday to monitor the patient's temperature continuously until final study closeout.
- Complete the event monitoring log every day.
- In the event of a hospital admission during the study period, the hospitalized subject will stop using the device. If the subject has contributed less than 50% of data (i.e. used the device for less than 7 days) prior to hospitalization, they will be dropped from the study and another subject will be recruited to make up the enrollment

target. However, subjects who have contributed at least 50% of data prior to hospitalization will stop using the device but will be included in final analyses.

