### 6.1 Primary and secondary endpoints

6.1a Primary outcome measurement: use feasibility of the iThermonitor will be assessed by ability of the device to successfully capture, transmit and display the patient's body temperature data on the study iPad mini. To limit recall bias, subjects will be required to log (Appendix 5) the ability to view the temperature data on the iPad mini once a day for the entire duration of the study. The device will be deemed a feasible continuous temperature monitoring tool if at least 80% of study subjects are able to successfully use the iThermonitor to monitor their body temperature. A subject must be able to view temperature data on the provided iPad mini at least 80% of the time in the study to be considered successful. "Time in the study" here is defined as the number of days the subject spends in the study which is expected to be two weeks.

6.1b Secondary outcomes: secondary outcomes which will be assessed at the end of the study include:

- i. Usability, acceptability and satisfaction with the iThermonitor. This will be assessed by questionnaires specifically designed for this study. We will be assessing ease of use, acceptability, connection and use problems like the device falling off the skin, usefulness of out-of-range temperature alerts and adverse reactions. We will also assess to see if the device helps to build caregiver self-efficacy skills in caring for the patient.
- ii. Caregiver engagement with the iThermonitor. This will be assessed by time to first measurement and upload from the time of discharge and also by the frequency of logins to the iThermonitor app.
- iii. Caregiver anxiety will be assessed using the GAD-7 questionnaire.

6.2 Sample size and statistical power or precision associated with the sample size: The length of time required to accrue an adequate number of subjects to the study should be indicated.

We will be able to estimate a feasibility success rate of 80% to within a 95% confidence interval of +/- 16% with a sample size of 25 evaluable patients. This is in keeping with a

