### 6.7 Analysis plan

Data collected will be verified before analysis, which will be done with Data Analysis and Statistical Software: STATA, version 13 with an alpha of 0.05 set a priori. All participants will be followed up for two weeks and we will summarize their baseline demographic and technology use characteristics.

To address the primary aim, the feasibility success rate will be calculated as the number of evaluable patients who meet the criteria for 'success' (per section 6.1) divided by the total number of evaluable patients. A 95% confidence interval will be calculated on this proportion. If the upper limit of the 95% confidence interval is less than 80%, then we will consider the iThermonitor not to be a feasible clinical decision support tool.

Descriptive analyses will be performed on all baseline data. Endpoints for all study outcomes are defined in section 6.1 above. All continuous variables will be computed as means with standard deviations, median and ranges while categorical variables will be computed as frequency distributions and percentages. The binomial test of proportion will be used to our dichotomous outcome of successfully using the iThermonitor. Paired t-test will be used to

analyze pre- and post- GAD-7 scores measured as a continuous variable. All other outcome variables will be summarized with descriptive statistics.

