#### 6.8 Handling of missing data in the analysis

We have adopted simple data collection techniques to limit missing data for this trial. Since this is largely exploratory work with descriptive statistics, a complete case analysis approach will be adopted for this study. .

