### iThermonitor Daily Event Monitoring Log

Please indicate **Yes** or **No** for each column everyday during the study.

Day	The iThermonitor stayed on the body for most of the day		I was able to view the temperature data on the iPad mini	
	Yes	No	Yes	No
1				
2				
3				
4				
5				
6				
7				
8				
9				
10				
11				
12				
13				
14				

Caregiver Signature \_\_\_\_\_ Date \_\_\_\_\_

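### For admitted children, 6.6 and 5.63 as worded set evaluability by days of device use, so a low-use child who fails 6.1 can be dropped and replaced instead of counted

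*Combined protocol and SAP*

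**What the plan says.** Section 6.6 stops device use when a child is admitted and then sorts admitted children by this test: "If the hospitalized subject has contributed less than 50% of data (i.e. used the device for less than 7 days) prior to hospitalization". Those who meet it are dropped and replaced; the others stay in the final analysis. Section 5.63 repeats it: "If the subject has contributed less than 50% of data (i.e. used the device for less than 7 days) prior to hospitalization". Neither section mentions days at home or days elapsed. The same list in 5.63 tells families: "Use the iThermonitor everyday to monitor" the child's temperature. On how many will be lost, 6.6 says: "We estimate that less than 20% of subjects enrolled in the study might be inevaluable".

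Under 6.1 a child succeeds if data can be viewed on the iPad mini for at least 80% of the time in the study, which "is defined as the number of days the subject spends in the study", expected to be two weeks. The device is feasible if at least 80% of subjects succeed. Under 6.7 the rate is the number of successes "divided by the total number of evaluable patients", and the device is not feasible if the upper 95% limit is below 80%.

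The daily log has one column for wear ("The iThermonitor stayed on the body for most of the day") and a separate one for viewing. On missing data, 6.8 says "a complete case analysis approach will be adopted for this study" and does not define a complete case.

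**The concern.** The test for entering the denominator is nearly the outcome itself. Section 6.6 gives its aim as seeing how the device is used at home, so poor use at home is a result of the study and not a reason to set a child aside. As worded, two children with the same poor use are treated differently: the one who is never admitted counts as a failure, while the one who is admitted is replaced by someone who may succeed. Two children admitted on the same day are also treated differently according to how well they used the device.

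At stake is the primary rate on 25 patients, where one result can decide whether the 80% criterion in 6.1 or the limit in 6.7 is met.

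**Working it through.** **The plan's own figure.** 1.96 × √(0.8 × 0.2 / 25) = 0.157, which rounds to the stated ±16% in 6.2. The calculation assumes 25 evaluable patients, so who is evaluable fixes the denominator.

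**Step 1: whom the rule removes.** Let H be home days before admission and U the days of use (U ≤ H). The rule removes every admitted child with U ≤ 6. Assumption: viewed days do not exceed use days. Success needs at least 0.8 × H viewed days, rounded up.

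| H | Viewed days needed | Best case among those removed | Under 6.1 |
|---|---|---|---|
| 5 | 4 | 5/5 = 100% | success |
| 6 | 5 | 6/6 = 100% | success |
| 7 | 6 | 6/7 = 85.7% | success |
| 8 | 7 | 6/8 = 75.0% | failure |
| 9 | 8 | 6/9 = 66.7% | failure |
| 10 | 8 | 6/10 = 60.0% | failure |
| 13 | 11 | 6/13 = 46.2% | failure |

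From H = 8 on, every removed child is a failure. A fixed 14-day denominator does not change that: 6/14 = 43%, with 12 days needed.

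**Step 2: two comparisons.**
- Against a home-day rule (drop if H < 7): both rules drop every child with H ≤ 6. The worded rule also drops those with H ≥ 7 and U ≤ 6, who under the assumption are all failures except 6/7.
- Against dropping nobody: early admissions who succeeded (5/5, 6/6) are removed as well as failures, so the direction is not fixed.

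**Step 3: the decision boundaries.** Had the failure been kept, no replacement would have been recruited and the denominator would still be 25.
- Reported 20/25 = 80% meets 6.1. With the failure kept, it is 19/25 = 76% if the replacement succeeded (criterion missed), and 20/25 if the replacement failed.
- Reported 16/25 has an exact upper limit of 82.0%. With the failure kept and a successful replacement removed, 15/25 has 78.9%, which is not feasible under 6.7. The plan names no interval method; with Wilson limits the step is from 17/25 (82.8%) to 16/25 (79.8%).

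**Step 4: illustration on assumed inputs.** None of these inputs is in the documents: 70% of families view on 97% of days and 30% on 40%; a use day is a viewed day; 20% of children are admitted, evenly over home days 1–13.
- Home-day rule: drops 20% × 6/13 = 9.2% of enrolled; expected rate 69.5%.
- Worded rule: drops a further 3.2%, of which 3.0% are failures. Total dropped 12.4%, inside the plan's estimate of under 20%. Expected rate (0.9077 × 0.6947 − 0.0020) / 0.8757 = 71.8%.
- Chance of 20 or more successes in 25: 25% against 18%. Chance of 16 or more (escaping the not-feasible finding, exact limits): 86% against 79%.

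Varying the assumptions:

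| Changed input | Worded rule | Home-day rule | Difference (points) |
|---|---|---|---|
| 10% admitted | 70.6% | 69.5% | 1.1 |
| 30% admitted | 73.2% | 69.5% | 3.7 |
| 20%, all before home day 7 | 69.5% | 69.5% | 0 |
| 20%, all from day 7 on | 73.5% | 69.5% | 4.0 |
| 30%, all from day 7 on | 75.6% | 69.5% | about 6 |
| 20%, weaker families view on 70% of days | 75.7% | 74.7% | 1.0 |

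**The case against.** **The rule may mean elapsed time.** Families are told to use the device every day, 5.1 fixes 14 days of collection, and 7 is half of 14. On that reading the rule asks only whether there was a week of home follow-up, and the selection disappears. The reading is possible. But the sentence in 5.63 is an instruction, and adherence to it is part of what the study tests. The explanatory phrase in 6.6 and 5.63 says use. If elapsed days were intended, the text still has to say so.

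**Use is not viewing.** The log records them separately, and nothing ties a use day to either column. Children who wear the device but cannot view data stay in as failures, so a reader who infers that the rule removes failures in general goes too far. This limits the point to low-use children admitted on home day 7 or later.

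**The rule loses successes too.** In the base illustration it drops more successes (6.7% of enrolled) than failures (5.7%). The rate still rises there, because failures are 46% of those dropped and about 30% of all children. That outcome depends on the inputs and does not establish a fixed direction against counting everyone.

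**The base illustration is pessimistic.** The plan hypothesises at least 80% success. With 20% weaker families instead of 30%, the chance of escaping the not-feasible finding is 98.8% against 97.9%, although the chance of 20 or more successes still moves from 59% to 67%. This stands: the effect on the 6.7 verdict can be negligible.

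**This is a small exploratory pilot.** True, but it has a stated pass mark, and the change costs a few sentences.

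**Conclusion.** The point holds as a defect of wording with a real consequence: 6.6 and 5.63 select admitted children on a quantity close to the outcome. Compared with a home-day rule, the extra children removed are nearly all failures, so the reported rate is raised. This rests on viewed days not exceeding use days, and on the literal meaning of use.

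The size is unknown, because the documents give no admission rate, timing or use pattern. The range of 0 to about 6 percentage points comes from assumed inputs and is not a forecast.

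Two stronger readings are tempting and are not supported. A reader might infer that one removed failure decides the trial. It does so only at a boundary, and only if the replacement succeeded. A reader might also add up to six dropped children to the denominator (6/31 = 19.4%, under the plan's 20%) and conclude that a reported 80% could hide 20/31 = 64.5%. That sum counts both the failures and their replacements, and it supposes that every dropped child was a low-use failure.

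The undefined complete case in 6.8 is missing detail, not a second demonstrated bias. It should be fixed. Confidence is moderate.

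**What to change.** - In 6.6 and 5.63, make an admitted child non-evaluable only if there were fewer than 7 calendar days at home before admission, whatever the use. Count from the scheduled start in 5.1 (the day after chemotherapy or discharge), not from first use. Section 5.1 also speaks of two weeks from the start of device use, so the amended text should name the start explicitly.
- Keep every other enrolled dyad in the primary denominator, including non-admitted dyads that start late or never start. Limiting the set to dyads that began use would remove failures that the plan now counts.
- Score evaluable admitted children on home days up to admission, with low use counted as failure.
- Add a sensitivity analysis of all enrolled dyads with dropped and replaced children counted as failures and, beside it, one with those children scored on their own home days.
- In 6.8, count a blank log day as not viewed in the primary analysis, with a sensitivity analysis that leaves blank days out.

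The cost is a few sentences in 5.63, 6.6 and 6.8, with no new data or patients. The reported rate may be lower, and some viewed but unlogged days will count as not viewed. Failures admitted before home day 7 still leave the primary denominator and appear only in the sensitivity analysis. The rule that admitted children stop using the device is not questioned.

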Neutropenia predisposes patients to significant risk for infectious complications which increases morbidity and mortality. Usually, fever is the first clinical sign of the inflammatory response to the infective process; and early detection is an indication for empiric antimicrobial therapy and further evaluation to determine risk for sepsis. Today, broad-spectrum antimicrobial therapy at the first detection of fever has helped significantly decrease the mortality associated with neutropenia in the intensive phase of chemotherapy. Therefore, early detection of fever, through regular temperature monitoring, in a neutropenic patient is critical to improved clinical outcome. Vigilance on the part of care providers and caregivers is crucial to early detection. Traditionally, this is simply done through episodic oral or axillary monitoring of temperature. In this study, we propose to test the use feasibility of an innovative device that continuously monitors body temperature as a clinical decision support tool in pediatric patients undergoing myelosuppressive therapies for acute leukemias and other childhood cancers.

The iThermonitor, a FDA class II device, is a high accuracy device that continuously captures body temperature and automatically delivers the data wirelessly (via blue tooth or wi-

fi) to mobile devices or for cloud storage. It has the capacity to store 10 days worth of recorded temperature data. The device can be used to effortlessly monitor patients on a continuous basis during the intensive phase of chemotherapy as opposed to the usual episodic oral or axillary measurements. It is also able to generate and deliver out-of-range temperature alerts on a mobile application for care givers or providers. It also provides care providers an opportunity to remotely monitor their patients' temperature in the immediate period after discharge from the hospital. Therefore, we hypothesize that the iThermonitor can serve as a feasible clinical decision support in the management of pediatric patients undergoing intensive treatments for acute leukemia and other childhood cancers. The device hasn't been previously tested for use in pediatric patients and finding from this study could generate useful data for future studies.

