## 2.2 Primary and Secondary aims:

2.21 The primary aim of this trial is to assess the use feasibility of the iThermonitor as a clinical decision support tool in the management of patients on myelosuppressive therapies for acute leukemia and other childhood cancers. We will consider the iThermonitor as a feasible clinical decision support tool if it successfully captures body temperature data, transmit and displays the data on the iPad mini in at least 80% of the study subjects. We will also assess the ability of the device to alert the caregiver if the temperature falls outside of pre-set range which is defined for all patients as temperature less than or equal to 96 and greater than or equal to 100.

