## 2.22 Secondary outcomes:

- Usability, acceptability and satisfaction with the iThermonitor.
- Caregiver engagement with the iThermonitor.
- Effect of the study on caregiver anxiety.

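### As written, a dyad admitted with under 7 days of device use leaves every result, so out-of-range, alert and engagement data recorded at home before admission are lost along with its place in the primary rate

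*Combined protocol and SAP*

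**What the plan says.** Section 5.63 states: "In the event of a hospital admission during the study period, the hospitalized subject will stop using the device". Sections 5.63 and 6.6 then give the same two-way rule. For a subject who has "contributed less than 50% of data (i.e. used the device for less than 7 days) prior to hospitalization", the consequence is "they will be dropped from the study and another subject will be recruited to make up the enrollment target". A subject with at least half of the data before admission, by contrast, "will stop using the device but will be included in final analyses". The reason given in 6.6 is that the study is about use at home. The section adds: "We estimate that less than 20% of subjects enrolled in the study might be inevaluable".

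Section 6.7 restricts the primary success rate to evaluable patients, describes all baseline data, applies a paired t-test to GAD-7, and summarises everything else descriptively. It names no population for the alert, engagement, usability or GAD-7 results. Section 6.8 adopts complete-case analysis. Section 6.7 also says that all participants are followed for two weeks, which does not fit a rule that removes some of them earlier.

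The results at stake are set out elsewhere. Within the primary aim, section 2.21 says: "We will also assess the ability of the device to alert the caregiver if the temperature falls outside of pre-set range". The table in 5.4 lists the number of out-of-range episodes. Section 6.1b lists usability and satisfaction, caregiver engagement (time to first measurement and upload, app logins) and GAD-7.

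**The concern.** The rule separates subjects who are in the final analyses from subjects who are out of the study. It does not separate those who count in one rate from those who do not. An interest in home use explains why device data stop at admission. It does not explain why data already recorded at home should go too.

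Removal depends on an event after enrolment that may be linked to what is being measured. Section 1.2 describes fever as usually the first sign of infection in neutropenia and says "early detection is an indication for empiric antimicrobial therapy and further evaluation to determine risk for sepsis". Section 3.1c excludes children with ongoing febrile illness or documented infection at entry, so the study can observe only fevers that arise on study. If some of those lead to early admission, the episodes that bear most directly on the alert function drop out of its summary, and nothing in the report would show how many.

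**Working it through.** **1. The plan's own precision figure.** Inputs from 6.2: 25 evaluable patients and a success rate of 80%. The Wald half-width is 1.96 × √(0.8 × 0.2 / 25) = 1.96 × 0.08 = 0.157, which rounds to the stated 16%. The figure reproduces. This point does not touch it, because the target of 25 evaluable patients stays.

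**2. How many dyads could be affected.** With 25 evaluable and d inevaluable, the 6.6 estimate requires d / (25 + d) < 0.20, so d < 6.25.
- d = 6: 6/31 = 19.4%, within the limit.
- d = 7: 7/32 = 21.9%, over the limit.

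So at most 6 of 31 enrolled dyads would be affected. This is an upper bound: the 6.6 figure is itself a ceiling, and subjects may be inevaluable for reasons other than early admission.

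**3. What exists for such a dyad at admission.**
- Temperature data: uploaded automatically through the paired receiver (5.4), so readings from before admission may already be stored. Out-of-range episodes can be read from them against the fixed limits in 5.3.
- Engagement: time to first upload and login frequency (6.1b) are available up to admission.
- Caregiver report of alerts: asked in the close-out survey (Appendix 4.1, statement 9 of question 1, and questions 16 and 17). The daily log (Appendix 5.2) has two columns, wear and viewing, and none for alerts. The plan describes no close-out for a dyad that is removed.
- GAD-7: taken at entry and close-out only (5.4). Before admission only the baseline score exists, and the paired test cannot use it alone.

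**4. Could the alert summary be selectively depleted?** The documents give no fever rate and no reasons for admission, so what follows is an illustration on assumed values, not an estimate. Let fr be the share of the 25 retained children with a fever and fd the share among the d removed. The fraction of all children with a fever who are lost is d·fd / (25·fr + d·fd).

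| Assumption | d = 6 | d = 3 |
|---|---|---|
| fd = fr (admission unrelated to fever) | 6/31 = 19% | 3/28 = 11% |
| fr = 30%, fd = 50% | 3/10.5 = 29% | 1.5/9 = 17% |
| fr = 10%, fd = 100% | 6/8.5 = 71% | 3/5.5 = 55% |

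In the first row the loss is only proportional to the dyads removed, and nothing is selectively depleted. If removed children had fewer fevers than retained ones, for example because their admissions were planned, the loss would be smaller still. The answer depends almost wholly on fd and fr, which the documents do not supply.

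**The case against.** The strongest reply is that the rule is pre-specified, has a stated rationale, and affects descriptive secondary results in a single-arm pilot of 25 on which no decision rule depends. The plan also never says outright that recorded data are discarded. Section 6.7 attaches evaluability only to the primary rate, and baseline data are described for all. This stands as a reason to treat the matter as a cheap correction of wording. It does not remove the point: the contrast between leaving the study and being kept in the final analyses, with no other set defined and complete-case analysis, leaves these data no place in the results.

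A reader might go further and infer that the rule takes out the children most likely to have had a fever and puts in children who stayed well. The documents do not support that. The rule covers admission for any reason, and section 4.1 shows that admission for chemotherapy is ordinary in this population. No admission rates, reasons or timings are given. Children admitted after at least 7 days of use are kept, and a replacement may itself be admitted later and kept.

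A reader might also infer that anxiety and satisfaction will look too favourable. That does not follow either. A caregiver whose alert caught a fever might rate the device higher, so removing that dyad could lower satisfaction.

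Three further objections stand. The alert range includes low temperatures, so alerts are not the same as fevers. Section 6.1 defines no alert-accuracy endpoint, so a few more partial records would add to a description but would not allow accuracy to be estimated. Adverse events are already documented and followed under 5.71 and 5.73.

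**Conclusion.** The point holds in a limited form. As written, the removal rule reaches beyond the primary rate, and no analysis set protects out-of-range, alert and engagement data recorded at home before an early admission. Section 1.2 makes a link between early admission and fever plausible, so the alert summary may be selectively depleted.

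The only size that rests on the plan's own figures is the ceiling of 6 dyads in 31 (19.4%). The size of any selective loss cannot be computed: the illustrated shares of 17% to 71% hold only under the assumed fever rates and should not be read as findings. The direction of any effect on satisfaction or GAD-7 is unknown. The primary rate and its stated precision are not called into question here.

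**What to change.** In 5.63, 6.6 and 6.7, replace the wording that removes the dyad from the study with: not counted in the primary success rate, and replaced for that rate only. Then:

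- Include every dyad that started the device in the descriptive summaries of out-of-range episodes, alerts and engagement, using data up to admission.
- Offer these caregivers the online close-out already provided for in 5.64, so that the usability and alert items can be summarised.
- Report the number of replaced dyads, with the timing and reason of each admission.
- For "Effect of the study on caregiver anxiety", keep the paired GAD-7 test on the planned set. Show any close-out GAD-7 from early-admitted caregivers separately, because its 2-week recall may span the admission.
- Reconcile the 6.7 statement that all participants are followed for two weeks with the revised rule.

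The rule that device use stops at admission is unchanged, as is the target of 25 evaluable patients. The cost is wording in three sections, up to about 6 more online close-outs and, if the sponsor chooses, up to 6 × $100 = $600 in payments. The downsides are that some close-outs will be incomplete and that the secondary set will be slightly larger than the primary set (up to 31 against 25), which the report should state.
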